## 1. Study Summary

Study Title	Randomized Controlled Trial To assess the Benefits of Dexcom Continuous Glucose Monitoring with Glucose telemetry System for the Management of Diabetes in Long-term Care Setting: The CGM-GTS in Long-term care
Study Design	Randomized Controlled Trial
Primary Objective	To compare differences in frequency of hypoglycemia (<70 mg/dl) and glycemic control (time in range [TIR] 80-180 mg/dl) between the Dexcom CGM with Glucose Telemetry System (CGM-GTS) compared to a standard of care protocol, in residents with T2D treated with insulin and/or insulin-secretagogues, in subacute and long-term skilled nursing care facilities.
Secondary Objective(s)	Determine differences in clinical outcomes (number of complications, ER visits and need for hospital re-admissions), and health care utilization between the use of real-time Dexcom CGM Glucose Telemetry System (CGM-GTS) compared to a standard of care in patients with T2D in subacute and long-term skilled nursing care facilities.
Research Intervention(s)/Interactions	POC testing or to real time Dexcom CGM with GTS for up to 60 days of admission.
Study Population	Adult residents with T2D in subacute and long-term skilled nursing care facilities treated residents with T2D treated with insulin and/or insulin-secretagogues.
Sample Size	100
Study Duration for individual participants	Length of admission to subacute and long-term skilled nursing care facilities or up to 60 days (whichever comes sooner)
Study Specific Abbreviations/ Definitions	T2DM: Type 2 Diabetes Mellitus OADs: oral antidiabetic medications CGM: continuous glucose monitor GTS: glucose telemetry system LTC: Long Term Care SSI: Sliding Scale Insulin
Funding Source (if any)	Dexcom, Inc.

## 2. Objectives

Diabetes is common in patients in subacute and long-term skilled nursing care facilities. Most patients with T2D are treated with insulin alone or in combination with oral antidiabetic agents, with reported high rate of iatrogenic hypoglycemia. The rate of hypoglycemia in sulfonylureas and insulin treated patients is reported ~ 30-40%, and the development of hypoglycemia has been associated with greater resource utilization and higher emergency room and hospital transfers compared to residents without hypoglycemia. The use of CGM has been shown superior to POC testing (standard of care) in detecting both hypo- and hyperglycemic events. The use of CGM with glucose telemetry system (CGM-GTS) with alarm reduces the frequency and time in hypoglycemia compared in insulin treated patients with T2D compared to POC. We propose to conduct a RCT to compare the efficacy of CGM-GTS in reducing hypoglycemia in high risk population with T2D treated with insulin and/or insulin-secretagogues in subacute and long-term skilled nursing care facilities

## 3. Background

**Prevalence of diabetes in older adults and subacute and long-term skilled nursing care facilities.** The prevalence of diabetes increases with age, and it is estimated that more than 20% of older adults aged 65-75 years and 40% of adults >80 years of age have diabetes. The prevalence of diabetes in older adults is expected to increase due to longer life expectancy and improve care of the population. The estimated prevalence of diabetes in subacute and long-term skilled nursing care facilities is reported to be ~ 20% to 34%, and in parallel to the increasing geriatric population, the number of LTC admissions is expected to rise.

**Diabetes treatment in LTC facilities.** The goals of diabetes care in older adults and in patients in subacute and long-term skilled nursing care facilities include control of hyperglycemia and its symptoms, prevention and treatment of diabetic complications, and maintenance or improvement of general health status. Studies in hospitalized patients with diabetes have shown that improvement in glucose control can reduce complications and are cost savings; however, no prospective studies have determined the impact of improving glucose control on clinical outcome in subacute and long-term skilled nursing care facilities (LTC). The management of diabetes in LTC residents is similar to that recommended for ambulatory patients with diabetes; however, several factors complicate the management of hyperglycemia in this population. LTC residents tend to be older and to have higher rates of comorbidities associated with aging such as functional disability, hypertension, coronary artery disease, cerebrovascular events, depression, cognitive impairment, urinary incontinence, and higher risk of falls. In addition, they often experience changes in nutritional intake, which increase the risk of hypoglycemia.

**Current guidelines and position statements on diabetes management in older adults**  are based on consensus opinions or from extrapolations from studies involving middle-aged patients with diabetes. The American Diabetes Association guidelines recommend that older adults who are functional, cognitively intact, and have longer life expectancy should receive diabetes care with goals similar to those developed for younger adults. In these subjects, a

HbA1c level <7.5%, a fasting glucose between 90-130 mg/dl, and a random glucose <180 mg/dl is recommended. Less intensive goals are recommended for patients with advanced complications, life-limiting comorbid illness, or cognitive impairment. Other organizations including the American Geriatric Society, European Diabetes Working Party for Older People guidelines, International Association of Gerontology and Geriatrics, the European Diabetes Working Party for Older People recommend a target HbA1c of <7.5% for patients without major comorbidities while a higher target of 7.6-8.5% is proposed for frail patients with high risk of hypoglycemia. These guidelines highlight the importance of improved glucose control and avoidance of side effects and hypoglycemia, as they are associated with increased risk of complications and mortality in patients with diabetes.

**Diabetes drug utilization in subacute and long-term skilled nursing care facilities (LTC).** There are twelve antidiabetic drugs with different mechanisms of action to treat patients with T2D. Metformin is recommended as first choice OAD agent for the management of patients with T2D; however, it may cause anorexia, nausea, diarrhea, weight loss, and lactic acidosis in patients with impaired renal function. Insulin secretagogues are effective in reducing glucose levels, but are associated with high risk of hypoglycemia. Thiazolidinediones improve insulin sensitivity but frequently cause weight gain, edema, osteopenia and are contraindicated in subjects with heart failure. The  $\alpha$ -glucosidase inhibitors delay carbohydrates absorption, but are associated with a high rate of GI side effects. DPP4-inhibitors are promising agents in the elderly because they stimulate insulin secretion in a glucose-dependent fashion, thus not causing hypoglycemia when used as monotherapy or in combination with metformin therapy.

Insulin therapy is widely recommended for diabetes management in LTC residents. Recent reports indicate that prescribing pattern in patients with diabetes in LTC facilities is shifting towards insulin, accounting for nearly 68% of new drug starts. Clinical guidelines recommend initiating insulin when oral agents fail or are contraindicated, and when random BG levels are >180 mg/dL. These guidelines favor the use of basal bolus insulin regimens over sliding scale regular insulin. The basal bolus insulin has been shown to improve glycemic control and to reduce hospital complications in patients with T2D; however, insulin administration approach is associated with high risk of hypoglycemia (see preliminary results).

**Glucose monitoring in subacute and long-term care settings: Capillary point of care (POC) and CGM glucose testing.** Bedside capillary POC glucose monitoring is the standard of care to assess glycemic control in the hospital and in LTC facilities. POC testing is usually performed before meals and at bedtime. CGM measures interstitial glucose every 5-15 minutes, thus provides a more complete glycemic profile during 24-hours than POC testing. Several randomized trials have shown that CGM systems facilitate and improve diabetes care in insulin-treated ambulatory patients, as well as in hospitalized patients. In a recent study of hospitalized patients with T2D, we reported increased detection of both hypo- and hyperglycemic events with the use of CGM compared to the standard-of-care POC BG testing. More than 50% of the hypoglycemic events occurred between dinner and breakfast; suggesting that these episodes would be missed by standard POC testing. In addition, a prospective

hospital study in insulin treated patients with T2D by our group reported that 45% of hypoglycemic events were asymptomatic . In multivariate analysis, male gender (OR 2.08, 95% CI 1.13 to 3.83, p=0.02) and age >65 years (OR 4.01, 95% CI 1.62 to 9.92, p=0.02) were independent predictors of asymptomatic hypoglycemia. A recent panel of experts in inpatient diabetes care reported that CGM could more effectively identify trends toward hypoglycemia and hyperglycemia, allowing for better and safer management of patients with inpatient hyperglycemia .

Recent reports indicate that CGM data can be transmitted to the nursing station by way of automatic downloading into a monitor at the nursing station. A recently published study evaluated whether the Dexcom CGM using a “Glucose Telemetry System” can decrease hypoglycemia in the general wards/non-ICU setting. The study included insulin treated patients with T2D at high risk for hypoglycemia. Participants were randomized to either the “Glucose Telemetry System” (intervention group) or to POC BG testing (control group). For patients in the “Glucose Telemetry System” nurses were instructed to proceed with hypoglycemia prevention actions if the low glucose alerts were activated (set at <85 mg/dl). Participants in the control group were placed on “blinded” CGM systems which were only used to collect glucometrics data. Overall, the subjects in the CGM-GTS experienced fewer events of hypoglycemia (<70 mg/dL), clinically significant hypoglycemia (<54 mg/dL) compared to the POC BG group. The outcomes of the intervention versus control groups for these two levels of hypoglycemia were, respectively, 0.67 versus 1.69 events/ patient, p =0.024 (< 70 mg/dl) and 0.08 versus 0.75 events/patient, p =0.003 (< 54 mg/dl). In addition, there was a reduction in percentage of time in hypoglycemic range <70 mg/dl and <54 mg/dl in the GTS compared to POC group (0.40%, versus 1.88%, p =0.002 and 0.05%, versus 0.82%, p =0.017). In the current research proposal, we will use the Dexcom G6 CGM with GTS and alarm set up at 85 mg/dL to prevent hypoglycemia.

### **Significance and Innovation.**

**Significance.** Two previous RCTs in the subacute and LTC facilities comparing oral agents and basal insulin reported similar improvement in glycemic control, but high rates of hypoglycemia in patients treated with basal insulin . The rate of hypoglycemia in insulin and sulfonylureas treated patients was 30-40%. Patients with hypoglycemia required greater resource utilization and higher emergency room and hospital transfers compared to residents without hypoglycemia . The high rate of insulin-associated hypoglycemia is worrisome, as recent population studies have suggested that diabetes prescribing in LTC is shifting towards insulin, accounting for ~half of patients with T2D  and nearly 68% of new drug starts . Capillary POC glucose testing is the standard of care for glucose monitoring in the hospital and LTC facilities. Our group and others have shown that POC misses about 40% of hypoglycemia cases, particularly at night (REF). Increased detection of both hypo- and hyper- glycemic events have reported with the use of CGM compare to the POC BG . In addition, we recently reported that CGM-GTS with alarm can successfully reduce the frequency and time in hypoglycemia compared in insulin treated patients with T2D compared to POC (REF). We anticipate that by Reducing hypoglycemia in subacute and long-term skilled nursing care facilities may reduce the rate of complications, ER visits and need for hospital readmissions.

[figure not shown]
**Innovation.** We propose the first RCT to assess the impact of glucose control and hypoglycemia reduction with the use of real time CGM with an alarm system to prevent hypoglycemia and facilitate the care of insulin and non-insulin treated patients with T2D in subacute and long-term skilled nursing care facilities. The results of this study have great potential to impact and facilitate care and to change current clinical guidelines in the management of older adults with diabetes in subacute and LTC facilities.

#### PRELIMINARY RESULTS:

[figure not shown]
**Diabetes and Clinical Outcome in LTC Residents** . In a retrospective study, we analyzed the quality of diabetes care, glycemic control, and clinical outcome in 1,409 subjects admitted to 3 community LTC facilities in Atlanta. The prevalence of diabetes was 34.2%. On admission, patients with diabetes were sliding scale regular insulin (25%), OADs (5%), insulin (34%), or with combination of OADs and insulin (26%). Patients with diabetes had higher number of complications and required more emergency room and hospital transfers. A total of 42% of patients had  $\geq 1$  episode of BG  $<70$  mg/dl and 7% had a BG  $<40$  mg/dl. Hypoglycemia was reported in 45% on OADs (mostly sulfonylurea plus SSI), or insulin therapy. Patients with hypoglycemia had a longer length of stay, higher emergency room or hospital transfers (44% vs. 30%;  $p=0.004$ ) and higher mortality (18% vs. 10%,  $p=0.015$ ). These results indicate that diabetes is common in LTC and is associated with higher resource utilization and complications, and that hypoglycemia is associated with increased rates of emergency room care and hospitalization, length of stay, and mortality.

**Comparing of Oral Antidiabetic Agents and Basal Insulin in LTC Residents with T2D** . In a prospective study we recruited 150 patients from 2 university-affiliated facilities with BG  $> 180$  mg/dl or A1C  $>7.5\%$ , treated with diet and/or with stable dose of OADs or glargin (starting at 0.1 U/kg/day), were randomized to continue OAD plus sliding scale insulin or to basal insulin glargin starting at 0.1 U/kg/day plus SSI for up to 6 months (Fig 1). There were no differences in daily glucose or with the A1C at 3 months or at 6 months or in the number of patients with hypoglycemia (basal 28% vs. control 31%,  $p=0.37$ ). The results of this study indicated similar improvement in glycemic control, without differences in mean daily BG, hypoglycemia with basal insulin or with OADs and SSI supplements. It was also evident that 1/3 od treated with OADs and insulin experienced hypoglycemia indicating the need for safer regimens.

Fig 1-Oral agents vs. Basal Insulin in LTC

B Hypoglycemia

**DPP4-inhibitors vs Basal insulin in LTC (Linagliptin-LTC Trial).** A 6-month open-label pilot randomized controlled trial compared the efficacy and safety of a DPP4-i (linagliptin) and basal insulin in subacute and LTC residents with T2D admitted to 3 institutions affiliated with Emory University. A total of 140 residents with T2D treated with oral antidiabetic agents or low-dose insulin (0.1 U/kg/d), with fasting BG>180 mg/dL and/or HbA1c >7.5% were randomized to linagliptin 5 mg day or glargin at a starting dose of 0.1 U/kg/d. Baseline antidiabetic therapy, except metformin, was discontinued on trial entry. BG was measured before meals and both groups received supplemental rapid-acting insulin before meals for BG > 200 mg/dL. As shown in Figure 4, treatment with linagliptin resulted in no significant differences in mean daily BG, but resulted in fewer mild hypoglycemic events <70 mg/dL (3% vs. 37%, P <0.001), and a non-significant trend towards lower risk of BG <54 mg/dL (0% vs 7%, p=0.06). There were no significant between-group differences in length of stay, complications, emergency department visits, or hospitalizations. These results suggested that DPP4-inhibitors are effective and represent an alternative to insulin therapy in many LTC residents with T2D.

**Continuous glucose monitoring (CGM) in the hospital setting.** Our research team have reported on 3 RCTs comparing the accuracy of using of CGM and capillary point of care (POC) glucose testing in insulin treated patients with T2D. Increased detection of both hypo- and hyper-glycemic events with the use of CGM compared to POC testing was found. More than 50% of the hypoglycemic occurred at night; suggesting that many of these episodes would be missed by standard POC testing. In a recent study, we compared the performance of the FreeStyle Libre Pro CGM and POC glucose testing among insulin-treated hospitalized patients with T2D. The mean daily glucose was higher by POC testing, and proportions of patients with BG <70 mg/dl and <54 mg/dl by POC BG were lower compared to CGM, all p<0.001 (Fig 3). The overall mean absolute relative difference (MARD), the statistical measure of accuracy used as the standard in glucose monitoring to represent performance, was 14.8%, ranging between 11.4 to 16.7% for glucoses between 70 and 250 mg/dl and the Error Grid analysis showed 98.0% of glucose pairs within Zones A and B.

In Figure 4, we present the accuracy of the Dexcom G6 CGM compared to POC testing in 218 consecutive insulin-treated general medicine (n= 192) and surgery (n= 26) patients with T1D (n= 9) and T2D (n=209). The mean age was 61 ±12 years, HbA1c 9.07±2.2%, admission BG 224±2 mg/dl, with 47% of patients with eGFR < 60 ml/min, length of stay, median 5.0 (4.0, 10.0) days. The Overall mean absolute relative difference (MARD) was 12.692 and median ARD of 10.048

Fig 2- Linagliptin vs Basal Insulin in

[figure not shown]

Fig 3. Hypoglycemia by POC and CGM

[figure not shown]
[figure not shown]

Fig 4. Accuracy Dexcom G6 in T2D, n=20a5

[figure not shown]
during the hospital stay and with 98.6% of matched pair readings within Error Grid within Zones A and B (Figure 4).

### Real Time CGM with Glucose

#### telemetry System.

We have conducted several clinical studies with GTS to transmit CGM data to the nursing station. A recently published study evaluated whether the Dexcom CGM using a “Glucose Telemetry System” can decrease hypoglycemia in the general wards/non-ICU setting. This

report is the first interventional RCT study of CGM to improve outcomes in the non-ICU setting. The study included patients with T2DM, who were at high risk for hypoglycemia. Participants were randomized to either the “Glucose Telemetry System” (intervention group) or to POC BG testing (control group). For patients in the “Glucose Telemetry System” nurses were instructed to proceed with hypoglycemia prevention actions if the low glucose alerts were activated (set at <85 mg/dL). Participants in the control group were placed on “blinded” CGM systems which were only used to collect glucometrics data. Overall, the subjects in the CGM-GTS experienced fewer events of hypoglycemia (<70 mg/dL), clinically significant hypoglycemia (<54 mg/dL) compared to the POC BG group. The outcomes of the intervention versus control groups for these two levels of hypoglycemia were, respectively, 0.67 versus 1.69 events/ patient,  $p =0.024$  (< 70 mg/dL) and 0.08 versus 0.75 events/patient,  $p =0.003$  (< 54 mg/dL). In addition, there was a reduction in percentage of time in hypoglycemic range <70 mg/dL and <54 mg/dL in the glucose telemetry system group compared to POC group (0.40%, versus 1.88%,  $p =0.002$  and 0.05%, versus 0.82%,  $p =0.017$ ).

Spanakis et al. Diabetes care 2020 (in press)

**Summary of Preliminary Data:** The result of studies demonstrates that hypoglycemia is common in insulin and non-insulin treated patients admitted to subacute and LTC facilities. Most of these episodes are missed when using capillary POC testing, with CGM providing a more complete assessment of glycemic status, detecting episodes of diurnal and nocturnal hypoglycemia compared to POC testing. The accuracy of Dexcom G6 is excellent and used together with GTS, reduces the frequency and time in hypoglycemia. The proposed RCT have great potential to impact and facilitate care of patients with diabetes in subacute and long-term LTC facilities, and might change current clinical guidelines in the management of patients with diabetes in subacute and long-term skilled nursing care facilities.

#### 4. Study Endpoints

Diabetes is highly prevalent among adults admitted to subacute and long-term skilled nursing care facilities (LTC) 1-4. Management of diabetes in these LTC facilities is challenging due to number of older adults with high prevalence of comorbidities, functional disability and altered nutritional intake, which increase the risk of hypoglycemia5-8.

Clinical guidelines from professional organizations 9-11 recommend the use of subcutaneous insulin, as the preferred therapy for glycemic control for most patients with type 2 diabetes (T2D) in LTC facilities. Although effective in improving glycemic control, observational and prospective randomized studies have reported rates of hypoglycemia between 30-37% with insulin administration in LTC residents with T2D 12,13. The high frequency of hypoglycemia is of great concern, as it has been associated with cardiac complications, emergency room visits, hospital admissions and mortality 14-16.

Bedside capillary point-of-care (POC) glucose monitoring is the standard of care to assess glycemic control in the in LTC facilities 17-19. POC testing is recommend by national guidelines before meals and at bedtime. This approach provides limited evaluation of glycemic excursions and to miss nocturnal hypoglycemia 20-23. Continuous glucose monitoring (CGM) measures interstitial glucose every 5-15 minutes, thus providing a more comprehensive 24-hours glycemic profile assessment than POC testing.

Recent studies from our group and others in hospitalized patients with T2D have reported increased detection of both hypo- and hyperglycemic events with the use of CGM compared to POC BG testing 21,23-25. We also reported that the hospital use of the Glucose Telemetry System with Bluetooth technology allows CGM glucose values to be transmitted from the patient's bedside to a central monitoring device in the nursing station, reducing the frequency of hypoglycemia in insulin treated patients with T2D 26,27. More recently, in collaboration with the University of Maryland, reported significant reduction in the rate of hospital hypoglycemia in insulin treated medicine and surgery patients with T2D using the glucose telemetry system with real-time CGM 28. In addition, the use of Dexcom G6 CGM in insulin-treated patients revealed great accuracy, with 98.6% of reading within Clarke error Grid A and B (unpublished data, see preliminary results section). Thus, our experience in the hospital supports the use of the use of CGM for the management of patients with diabetes and prevention of hypoglycemia. However, we do not know if this experience can be extrapolated to individuals in long-term skilled nursing facilities. Therefore, in-depth analyses of glycemic control and potential benefit of RT-CGM in real-world is needed to determine whether the CGM-GTS can improve glycemic control and prevent hypoglycemia in vulnerable population of adult patients admitted to LTC facilities.

The primary aim is difference between POC testing and CGM-GTS in the frequency of hypoglycemia (safety outcome) and glycemic control (efficacy outcome) during admission.

- 1) Hypoglycemia <70 mg/dl and clinically significant hypoglycemia <54 mg/dl (safety outcome)
- 2) Glycemic control, as measured by time in range (TIR) between 80-180 mg/dl (efficacy outcome)

[figure not shown]
**Secondary outcomes** include differences between groups in any of the following measures:

1. Nocturnal hypoglycemia < 70 mg/dl and < 54 mg/dl (between 22:00 and 06:00)
2. Number of hypoglycemia events (< 70 and 54 mg/dl)
3. Time in hypoglycemia (<70 mg/dl) and hyperglycemia (>240 mg/dl)
4. Number of prolonged hypoglycemia > 1 and 2 hours by CGM
5. Frequency and time of hypoglycemic during the day and night
6. Frequency and duration or time on hyperglycemia > 240 mg/dl
7. Percentage of BG readings within target BG of 70 and 180 mg/dl
8. Glycemic variability calculated by standard deviation and MAGE
9. Number of sensor removal for procedures/imaging, sensors failures, sensors dislodgments

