The present aims of this RCT is to investigate whether the Dexcom G6 CGM with Glucose Telemetry System (CGM-GTS) with hypoglycemia alarm may reduce the risk of hypoglycemia < 70 mg/dl (safety outcome) and improve glycemic control as measured by the percent of time in range (TIR) 70-180 mg/dl (efficacy end-point) in patients with T2D in subacute and long-term skilled nursing care facilities. Patients in the standard of care group will wear a blinded CGM and receive POC testing before meals and bedtime, with providers adjusting oral agents or insulin dose based on POC results. Patients in the intervention CGM group will have a single daily fasting POC testing and will wear a real-time Dexcom G6 with GTS, and providers will adjust oral or insulin therapy based on CGM-GTS profile information. [name], PhD at the School of Public Health at Emory University will conduct statistical analyses.

For the safety endpoint, we will first compare the proportions of patients who have at least one episode of hypoglycemia by POC and by CGM. We will first perform nonparametric comparisons of the rate of hypoglycemia based on a two-sided Chi-square test (or Fisher's exact test in the presence of low incidence rates), followed by the Cochran-Mantel-Haenszel test, which adjusts for the potential center effect. Then we will perform univariate Poisson regression (or Negative Binomial regression) to assess whether there is any difference in the number of clinically significant hypoglycemia events between the two treatment groups. We will further conduct multivariate Logistic regression, Poisson regression (or Negative Binomial regression) to estimate the difference in the rate and frequency of hypoglycemia while adjusting for potential confounders. A glucose value < 70 mg/dl is considered as hypoglycemia requiring a nurse-driven response; thus, a BG <70 mg/dl will be used for sample size calculation. Data from Singh et al a reduction of hypoglycemia was reported comparing the CGM/GTS system than POC (Singh et al 2020) per patient (0.67 episodes per patient, 95% CI 0.34-1.30

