versus 1.69 episodes per patient, 95% CI 1.11-2.58,  $p= 0.024$ ) . Based on the results of the recent glargine U100 vs U300 study using CGM monitoring in the hospital, 56% had CGM BG readings <70 mg/dl (vs 14% with POC testing-standard of care), it is reasonable to assume 60% of resident on LTC facilities will experience one or more BG < 70 mg/dl by CGM. If we assume that 35% in the standard of care group will have at least one BG <70 mg/dl (based on linagliptin LTC study) , using one-sided, two-sample t-tests, we require we will need 70 patients per group to achieve 80% power.

Hypoglycemia incidence, Rate in the CGM intervention group	30%	35%	40%	45%	50%
Estimated sample size (N/group) for 80% power	49	70	107	186	407

For the efficacy endpoint, we will compare mean daily glucose levels measured by CGM or POC, and percent TIR measured by CGM between treatment groups by nonparametric Wilcoxon-tests or two-sample t-tests, and by multivariate linear regression, which adjusts for other potential confounders such as age, gender, BMI, center, and admission HbA1c. A logarithm transformation may be employed to make the data better conform to the normality assumption. When conducting multivariate regression analyses, we will apply standard variable selection and model checking procedures to decide the final model. Stepwise, backward, or forward model selection strategy will be adopted to determine the variables to be included in the final model. Standard diagnostic and model checking procedures, such as deviance residual plot and Hosmer- Lemeshow test, will be applied to examine the fit of the developed models. To show non-inferiority between POC and CGM in terms of glycemic control, we set the equivalence margin of 18 mg/dl (1 mosm/l), from a view that a difference <18 mg/dl is usually not considered as clinically significant . Based on the results from our recent CGM trials , it is reasonable to assume the standard deviation of mean daily BG is bounded above by 45 mg/dl. Assuming the true BG difference between the treatment groups is zero, and using one-sided, two-sample t-tests, we require 70 subjects for each treatment group to achieve 80% power.

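### Two or three primary outcomes carry no testing order, alpha allocation or all-must-succeed rule, and the plan does not say which hypoglycemia measure decides

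*Combined protocol and SAP*

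**What the plan says.** Section 4 (Study Endpoints) defines the aim this way: "The primary aim is difference between POC testing and CGM-GTS in the frequency of hypoglycemia (safety outcome) and glycemic control (efficacy outcome) during admission". Two numbered items follow. The first is "Hypoglycemia <70 mg/dl and clinically significant hypoglycemia <54 mg/dl (safety outcome" and the second is "Glycemic control, as measured by time in range (TIR) between 80-180 mg/dl (efficacy outcome". Section 1 and the opening of the statistical text in Section 18 name only <70 mg/dl and TIR as the main measures. Section 18 gives the TIR range as 70-180 mg/dl, whereas Sections 1 and 4 give 80-180.

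For hypoglycemia, Section 18 states: "we will first compare the proportions of patients who have at least one episode of hypoglycemia by POC and by CGM". The tests are a "two-sided Chi-square test (or Fisher's exact test in the presence of low incidence rates), followed by the Cochran-Mantel-Haenszel test", which adjusts for center. Counts come next: "Then we will perform univariate Poisson regression (or Negative Binomial regression". Adjusted logistic and count models follow.

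For glycemic control, "we will compare mean daily glucose levels measured by CGM or POC, and percent TIR measured by CGM", by Wilcoxon or t-test and then by linear regression with stepwise, backward or forward selection. TIR therefore has one glucose source, CGM. Hypoglycemia and mean daily glucose have two. Section 18 also plans a non-inferiority comparison with an 18 mg/dl margin, sized on mean daily glucose.

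The only alpha in the document is in Section 19: two-sided <0.01, for stopping on death and hospital complications. The same paragraph plans interim analyses of the primary endpoint every 6 months and/or at half of randomization.

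**The concern.** When several outcomes are primary, the plan has to say what counts as a positive trial. It could require all of them, test them in a set order, or split alpha. This plan does none of these, so the error rate of a primary claim is undefined. For hypoglycemia the gap goes further, because the plan does not say whether POC or CGM decides, or which test does.

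The choice of source matters because detection by POC differs between arms by design. Under Section 6, controls have POC before meals and at bedtime, while the CGM group has one scheduled fasting POC a day. Section 15 adds POC checks when an alarm sounds, and control alarms are switched off. A POC-based difference could therefore reflect how often, and when, each arm is tested. CGM is worn in both arms.

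Calling hypoglycemia a safety outcome does not remove the issue. Sections 2, 5 and 18 make reducing it the purpose of the trial, so it is a benefit claim.

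**Working it through.** **1. Which significance level?** None is stated for the primary outcomes, so I inferred it from the Section 18 sample-size table (reference rate 60%, 80% power). With d = 0.60 − 0.35 = 0.25 and mean rate 0.475:

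- Uncorrected n = [1.96·√(2·0.475·0.525) + 0.8416·√(0.60·0.40 + 0.35·0.65)]² / 0.25² = 61.4.
- With continuity correction, n = (61.4/4)·[1 + √(1 + 4/(61.4·0.25))]² = 69.2, rounded up to 70. The table has 70.
- The same formula at 30, 40, 45 and 50% gives 48.4, 106.7, 185.9 and 407.1. The table has 49, 107, 186 and 407.
- One-sided 0.05, as the text describes the test, gives 49 per group at 35% (56 with correction).

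The table is therefore consistent with two-sided 0.05, and I use that level below.

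**2. How many primary outcomes?** Two by Sections 1 and 18 (<70 mg/dl and TIR). Three by Section 4 if <54 mg/dl is counted separately.

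**3. Family-wise error.** Assumptions: no true effect on any outcome, one test per outcome, any one win counts.

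- Independent, either direction: 1 − 0.95² = 9.75% for two outcomes; 1 − 0.95³ = 14.3% for three.
- Independent, favourable direction only (0.025 per test): 1 − 0.975² = 4.9%; 1 − 0.975³ = 7.3%.

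The correlations are not in the documents. I simulated equicorrelated normal test statistics over an assumed range:

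| Correlation | Two, either direction | Three, either direction | Two, favourable | Three, favourable |
|---|---|---|---|---|
| 0 | 9.7% | 14.3% | 4.9% | 7.3% |
| 0.5 | 9.1% | 12.6% | 4.5% | 6.3% |
| 0.8 | 7.8% | 9.8% | 3.9% | 4.9% |

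One test alone gives 5% in either direction and 2.5% in the favourable direction.

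**4. Methods and sources.** These figures count outcomes only. If the deciding result could also be chosen among POC and CGM, proportion and count, or unadjusted and selected models, the chance of at least one win cannot fall and will generally rise. The size of that rise depends on event rates and correlations that the documents do not give, so I put no number on it.

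**The case against.** The strongest reply is that the trial intends a joint claim: less hypoglycemia without worse glycemic control. The non-inferiority analysis of mean daily glucose in Section 18 fits that reading, and a claim that needs every component to succeed has no inflation. The reply stands this far: the any-win rule behind the figures is an assumption. The documents neither state it nor exclude it. They do not state the joint rule either, and non-inferiority on mean glucose is not the superiority-type comparison of TIR listed as primary.

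A second reply is that <70 mg/dl was used for sizing and that the methods come in an order. Both are true. But Section 18 gives <70 mg/dl that role only for the sample size, and the sequence words order methods within an outcome, not hypotheses. It is also fair that event counts are secondary outcome 2 in Section 4, although Section 18 analyses them under the safety endpoint.

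A third reply is that independence between <54 and <70 mg/dl is implausible, since every patient with a value <54 also has one <70. That stands, so 14.3% is an upper bound for one test per outcome.

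A reader might go further and infer that each primary outcome is tested from two glucose sources, or that 10-14% measures outcomes, methods and sources together. The documents do not support either. TIR is by CGM only, and 10-14% covers only the number of outcomes, in either direction, if there are three.

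**Conclusion.** The gap is real and should be closed. The plan has two primary outcomes, or three if <54 mg/dl is counted, and no rule linking them to a conclusion. It does not name the deciding source or test for hypoglycemia.

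The family-wise error is about 8-10% for two outcomes and 10-14% for three. For favourable wins alone it is about 4-5% and 5-7%, against 2.5% for one test. These ranges rest on an any-win rule, one test per outcome, an inferred two-sided 0.05, and assumed correlations between 0.8 and 0. Freedom over methods and sources adds an amount that cannot be derived from the documents.

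A reader might conclude that the plan permits any significant result to be reported as primary success, or that the false-success rate is known to be near 14%. The plan is silent on the first, and the second holds only at the top of one range. Section 3 speaks of potential to change guidelines, not of an established claim. What is at stake is that the trial would have no defined error rate to support such a change.

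**What to change.** State a fixed sequence at two-sided 0.05, each step claimed only if the one before is significant:

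1. Proportion with at least one CGM glucose <70 mg/dl, by the center-stratified Cochran-Mantel-Haenszel test already listed.
2. CGM TIR, after reconciling 80-180 (Sections 1 and 4) with 70-180 (Section 18), by one pre-named test such as the Wilcoxon test.
3. Proportion with at least one CGM glucose <54 mg/dl, if it is kept as primary, by the same test as step 1.

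Label POC-based comparisons, event counts and models with selected covariates as supportive. State whether mean-daily-glucose non-inferiority is a separate supportive claim or a step in the sequence. State that the interim looks in Section 19 will not be used to claim efficacy, or else allocate alpha to them. Without that, the sequence alone does not secure 5%.

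The cost is SAP wording, with no added patients. A Bonferroni split would instead raise the 70 per group to 83 (two tests at 0.025) or 90 (three at 0.0167), by the formula above. The downside of the sequence is that if step 1 is not significant, TIR and <54 mg/dl become exploratory. The order of steps 2 and 3 is a judgement for the sponsor, to be fixed before any comparative data are seen.
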